9.3. Definitions

9.3.1. Adverse Event (AE)

An AE is defined as any untoward medical occurrence in a patient (or study subject) who has received a pharmaceutical product; an AE does not necessarily have to have a causal relationship with this treatment. An AE can be any unfavorable or unexpected sign (e.g. an abnormal laboratory finding), symptom, or disease temporally associated with the use of a medicinal product, whether or not considered related to the medicinal product (ICH E2A Guideline – Clinical Safety Data Management: Definitions and Standards for Expedited Reporting, Oct 1994).

It is the responsibility of each investigator, based on his/her knowledge and experience, to determine whether a sign, symptom or abnormal finding should be considered an AE.

9.3.2. Serious Adverse Event (SAE)

An SAE is defined as any untoward medical occurrence that at any dose:

- Results in death
- Is life-threatening
- Requires inpatient hospitalization or prolongation of existing hospitalization
- Results in persistent or significant disability/incapacity
- Is a congenital anomaly/birth defect, or

- Is an important medical event

Note: The term “life-threatening” in the definition of “serious” refers to an event in which the subject was at risk of death at the time of the event; it does not refer to an event which hypothetically might have caused death if it were more severe (ICH E2A Guideline. Clinical Safety Data Management: Definitions and Standards for Expedited Reporting, Oct 1994).

Medical and scientific judgment should be exercised in deciding whether expedited reporting is appropriate in other situations, such as important medical events that may not be immediately life-threatening or result in death or hospitalization but may jeopardize the subject or may require intervention to prevent one of the other outcomes listed in the definition above. Examples include allergic bronchospasm, convulsions, and blood dyscrasias or development of drug dependency or drug abuse.

Note:

- A procedure is not an AE or SAE, but the reason for the procedure may be an AE or SAE.
- Pre-planned (prior to signing the ICF) surgeries or hospitalizations for pre-existing conditions which do not worsen in severity are not SAEs.

9.3.3. Adverse Event Severity

The following definitions should be used to assess severity of AEs:

- Mild: Awareness of sign or symptom, but easily tolerated, i.e. does not interfere with subject’s usual function.
- Moderate: Discomfort enough to cause interference with usual activity.
- Severe: Incapacitating with inability to work or do usual activity i.e. interferes significantly with subject’s usual function.

9.3.4. Causality Assessment

The relationship between an AE and the study products will be determined by the investigator on the basis of his/her clinical judgment and the following definitions:

- 1 = Related:
 - The AE follows a reasonable temporal sequence from study drug administration, and cannot be reasonably explained by the subject’s clinical state or other factors (e.g. disease under study, concurrent diseases, and concomitant medications).
 - The AE follows a reasonable temporal sequence from study drug administration, and is a known reaction to the drug under study or its chemical group, or is predicted by known pharmacology.
- 2 = Not Related:

- The AE does not follow a reasonable sequence from study product administration, or can be reasonably explained by the subject's clinical state or other factors (e.g. disease under study, concurrent diseases, and concomitant medications).

9.3.5. Action Taken Regarding the Investigational Product

- 1 = Dose Not Changed: No change in study drug dosage was made.
- 2 = Drug Withdrawn: The study product was permanently stopped.
- 3 = Dose Reduced: The dosage of study product was reduced.
- 4 = Drug Interrupted: The study product was temporarily stopped.

9.3.6. Adverse Event Outcome

- 1 = Recovered/Resolved
 - The subject fully recovered from the AE with no residual effect observed.
- 2 = Recovered/Resolved with Sequelae
 - The residual effects of the AE are still present and observable.
 - Identify sequelae/residual effects.
- 3 = Not Recovered/Not Resolved
 - The AE itself is still present and observable.
- 4 = Fatal

9.3.7. Other Action Taken for Event

Other Action Taken for Event will be reported as one of the following:

- 1 = None.
 - No treatment was required.
- 2 = Medication required.
 - Prescription and/or over the counter medication was required to treat the AE.
- 3 = Other.

9.4. Serious Adverse Event Reporting Procedure for Investigators

9.4.1. Reporting by Investigators

All AEs, SAEs, endpoints, and events of special interest, will be reported in the eCRF.

The following types of events should be reported in eCRF within 24 hours of awareness:

- SAEs (see Section [9.3.2](#) for definition)

- Hepatic events meeting combination abnormalities [ALT or AST $\geq 3 \times$ ULN with simultaneous total bilirubin $\geq 2 \times$ ULN] (potential Hy's Law case), both serious and non-serious
- Any event meeting the stopping rules for individual subjects per Section [3.1.6.1](#)

All events (serious and non-serious) must be reported with investigator's assessment of the event's seriousness, severity, and causality to study drug. A detailed narrative summarizing the course of the event, including its evaluation, treatment, and outcome should be provided. Specific or estimated dates of event onset, treatment, and resolution should be included when available. Medical history, concomitant medications, and laboratory data that are relevant to the event should also be summarized in the narrative. For fatal events, the narrative should state whether an autopsy was or will be performed, and include the results if available. Source documents will be retained in site's files and should not be submitted to the Sponsor for SAE reporting purposes.

Urgent safety queries must be followed up and addressed promptly. Follow-up information and response to non-urgent safety queries should be combined for reporting via eCRF to provide the most complete data possible within each follow-up.

In the event that eCRF is unavailable, report SAEs by faxing the paper Serious Adverse Event Report (SAVER) Form to CRO using the provided fax cover sheet and the appropriate fax number provided for your country. Once eCRF becomes available, please enter SAEs reported on the SAVER Form into eCRF as soon as possible. Please refer to eCRF Completion Guide for additional instructions.

Please call the local SAE Hotline or your study monitor for any questions on SAE reporting.

9.4.2. Notifying Regulatory Authorities, Investigators, and Institutional Review Boards/Institutional Ethics Committees

Daiichi Sankyo and/or designee will inform investigators, IRBs/IECs, and regulatory authorities of any suspected unexpected serious adverse event reactions (SUSARs) occurring in other study centers or other Daiichi Sankyo studies of the investigational product, as appropriate per local reporting requirements.

In the US, upon receipt of the sponsor's notification of SUSARs that occurred with the investigational product, unless delegated to the Sponsor, it is the investigator's responsibility to inform the IRB per the Sponsor's instruction.

In the European Economic Area member states, it is the Sponsor's responsibility to report SUSARs to all IECs.

9.5. Exposure In Utero During Clinical Studies

Daiichi Sankyo must be notified of any subject who becomes pregnant while receiving or within 4 weeks of discontinuing the investigational product.

Although pregnancy is not technically an AE, all pregnancies must be followed to conclusion to determine their outcome. This information is important for both drug safety and public health concerns. It is the responsibility of the investigator, or designee, to report any pregnancy in a female subject via the Exposure in Utero (EIU) Reporting form (please contact your study monitor to receive the form). The investigator should make every effort to follow the subject until completion of the pregnancy. If the outcome of the pregnancy meets the criteria for immediate classification as a SAE (i.e. post-partum complications, spontaneous abortion, stillbirth, neonatal death, or congenital anomaly, including that in an aborted fetus), the Investigator should follow the procedures for reporting SAEs outlined in Section 9.4. Elected abortion is a procedure and should be reported following the definitions and procedures for reporting AEs or SAEs.

9.6. Clinical Laboratory Evaluations

Blood and urine samples for clinical laboratory evaluations will be shipped to a central laboratory for analysis. Results of all laboratory tests will be reported in the subject's eCRF or merged electronically with the clinical database (see [Appendix 17.3](#)).

9.6.1. Hematology

A single 2 mL ethylenediaminetetraacetic acid (EDTA) tube of blood will be drawn for the hematology assessments listed in Table 9.1. These will be measured from samples obtained at the Screening/Baseline visit, Treatment visits, and End-of-Treatment/Early Termination visit.

Table 9.1: Hematology Analytes

Hemoglobin
Hematocrit
Red blood cell (RBC) count (with indices)
White blood cell (WBC) count (with differential)
Platelet count

9.6.2. Blood Chemistry

A 2.5 mL serum separating tube of blood will be drawn for the blood chemistry assessments listed in [Table 9.2](#). These will be measured from samples obtained at the Screening/Baseline visit, Treatment visits, and End-of-Treatment/Early Termination visit.

Table 9.2: Blood Chemistry Analytes

Sodium	Lactate Dehydrogenase
Potassium	Creatinine
Magnesium	Blood urea nitrogen
Bicarbonate	Total protein
Calcium	Albumin
Inorganic phosphorus	Uric acid
AST	Creatine kinase
ALT	Total cholesterol
Alkaline phosphatase	Triglycerides
Total bilirubin ^a	

^a Total bilirubin should be fractionated at baseline and whenever total bilirubin > 2 x ULN
 Abbreviations: ALT = alanine aminotransferase; AST = aspartate aminotransferase; ULN = upper limit of normal

9.6.2.1. Estimation of Creatinine Clearance

Creatinine clearance (CrCl) will be estimated from serum creatinine by the central laboratory using the Cockcroft-Gault equation ([Appendix 17.2](#)).

9.6.3. Urinalysis

Standard urinalysis including a microscopic examination will be conducted for all subjects at the Screening visit, Treatment visits, and End-of-Treatment/Early Termination visit (Table 9.3).

Table 9.3: Urinalysis Determinations

Specific gravity	Blood
pH	RBC
Protein	WBC
Glucose	Bilirubin
Ketones	Urobilinogen

Abbreviations: RBC = red blood cell; WBC = white blood cell

For samples with findings on macroscopic analysis, microscopic examination for red blood cells (RBCs), white blood cells (WBCs), bacteria, and casts should be performed.

9.6.4. Pregnancy Testing

A serum pregnancy test will also be performed for all women at all clinic visits through the End-of-Treatment/Early Termination visit. A urine pregnancy test will be performed for all WOCBP at the Follow-up clinic visit.

9.7. Vital Signs

Vital signs will be recorded at all visits and will include temperature, heart rate, and supine and orthostatic blood pressure.

For measurement of supine blood pressure, subjects should be in a supine or semi-recumbent position for a minimum of 5 minutes before the blood pressure measurement. Measurement of orthostatic blood pressure should follow measurement of supine blood pressure. Subjects should be asked to stand for 3 minutes before measurement of orthostatic blood pressure. Measurement of blood pressure should be conducted using a calibrated manometer or automatic inflatable cuff monitor; the blood pressure cuff should be kept in place between supine and orthostatic blood pressure measurements.

Blood pressure should be measured using the same arm and measuring device that was used in the preceding study. For subjects not completing a preceding study, the Screening visit (Visit 1) only, a blood pressure reading should be taken in both arms (unless there is a medical reason not to use a particular arm). The arm with the higher systolic reading should then be used throughout the rest of the study.

Blood pressure should be recorded to the nearest 2 mmHg mark on the manometer or to the nearest whole number on an automatic device.

9.8. Electrocardiograms

A 12-lead ECG will be conducted at the Screening visit (Visit 1) for de novo subjects, and at Start-of-Treatment visit (Visit 4) and at the End-of-Treatment/Early Termination visit (Visit 21) for all subjects. ECG recordings should be assessed as normal or abnormal, and any abnormal findings should be assessed as not clinically significant or significant. Clinically significant abnormal findings should be reported as medical history (if pre-existent). Refer to Section 9.1 for general guidance on when to report abnormal findings as AEs.

9.9. Physical Findings

9.9.1. Body Height and Weight

For de novo subjects only, measurement of height will be performed at the Screening visit (Visit 1) with the subject in a standing position and with shoes removed. The subject's knees should be straightened, head held erect, with eyes forward.

Measurement of weight should be performed at every visit, except the Baseline visit (Visit 3) for de novo subjects, with the subject dressed in indoor clothing, shoes removed. Subjects should be weighed on the same scale at all visits.

9.9.2. Physical Examinations

A full physical examination, with the exception of pelvis, breast, and rectum in women and the genitourinary system and prostate in men, will be performed at the Screening visit (Visit 1) for de novo subjects or at the Start-of-Treatment visit (Visit 4) for rollover

subjects and End-of-Treatment/Early Termination visit (Visit 21) for all subjects. An abbreviated physical examination will be performed at the Treatment visits.

The full physical examination should minimally include clinical evaluations of the head, neck, thyroid, eyes, ears, nose, throat, heart, lungs, lymph nodes, abdomen, skin, extremities, and musculoskeletal system.

For de novo subjects, a fundoscopy examination of the eyes, with pupil dilation or a scanning laser ophthalmoscopy examination, will be conducted at the Screening visit (Visit 1) and End of Treatment visit (Visit 21) during the full physical examination. At Visit 14 (Week 24), the abbreviated physical examination will include a fundoscopy examination without pupil dilation or a scanning laser ophthalmoscopy examination.

The abbreviated physical examination should minimally include clinical evaluations of the heart and lungs. Additional systems may be examined based on any symptoms exhibited by the subject.

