1.3. Risks and Benefits for Study Subjects

The results from nonclinical and clinical studies suggest that subjects treated with DS-5565 may experience improvement in pain associated with FM.

Anticipated risks of DS-5565 include the occurrence of adverse reactions related to central nervous system depression, such as dizziness and somnolence, as well as peripheral edema. Other notable TEAEs that have been observed in Phase 1 and Phase 2 studies include elevations of hepatic transaminases and suicide. For the approved $\alpha_2\delta$ ligands, in addition to dizziness, somnolence, and peripheral edema, certain adverse reactions requiring caution have also been reported, including but not limited to: weight gain, ophthalmologic disorders, suicidal behavior and ideation, angioedema, hypersensitivity, abrupt or rapid discontinuation, abuse potential, congestive heart failure, renal failure, and creatine kinase elevations.

A detailed description of efficacy and safety data related to DS-5565, including the results of Phase 1 and Phase 2 clinical studies of DS-5565, is provided in the DS-5565 Investigator Brochure. Safety monitoring procedures described in the protocol are considered to be adequate to protect subject safety.

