5.1.1. Method of Assigning Subjects to Treatments and Blinding

Subjects entering into the open-label extension phase of the study will initially receive a 15 mg QD dose of DS-5565. After 3 weeks on the 15 mg QD dose (at Visit 6, Week 3), subjects will be asked about the adequacy of their pain control. Depending on their level of pain control and whether they have experienced any clinically relevant TEAEs since the previous visit, subjects may be dose-escalated to DS-5565 15 mg BID. The dose escalation criteria are defined in Table 5.1.

Table 5.1: Dose Escalation Criteria

Pain Control ^a	Clinically Relevant TEAE ^b	Dose Increase ^c
Inadequate	No	Yes
	Yes	No
Acceptable but not optimal	No	Yes
	Yes	No
Optimal	No	No
	Yes	No

^a Based upon the investigator's judgment

^b Any moderate or severe episode of dizziness or somnolence, any episode of edema or clinically significant weight gain, or any other clinically relevant (in the judgment of the investigator) TEAE since the previous visit

^c Yes = subject may be dose-escalated to DS-5565 15 mg BID

Abbreviations: BID = twice daily, TEAE = treatment-emergent adverse event

Once a subject has been dose-escalated to 15 mg BID, continuation of the 15 mg BID dose will occur as long as pain control is adequate and the subject experiences no moderate or severe episode of dizziness or somnolence, edema, clinically significant weight gain, or any other clinically relevant (in the judgment of the investigator) AE. If the subject does experience a clinically relevant AE, then the following criteria will determine whether discontinuation or down-titration of the dose should occur:

- If the subject previously reported inadequate pain control with 15 mg QD dosing, the subject will be discontinued from the study
- If the subject previously reported acceptable pain control with 15 mg QD dosing, the subject may be dose-reduced to 15 mg QD

No blinding will be used.

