At each visit, the investigator should determine whether any AEs have occurred by evaluating the subject. AEs may be directly observed, reported spontaneously by the subject, or by questioning the subject at each study visit. Subjects should be questioned in a general way, without asking about the occurrence of any specific symptoms. The Investigator must assess all AEs to determine seriousness, severity, and causality, in accordance with the definitions in Section 9.3. The Investigator's assessment must be clearly documented in the site's source documentation with the Investigator's signature.

Investigators should follow subjects with AEs until the event has resolved or the condition has stabilized. Unresolved AEs, including significant abnormal laboratory values at the end of the study, should be followed up until resolution or until no longer clinically relevant.

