11.2. General Statistical Considerations

The statistical package SAS[®] (Version 9.2 or higher) will be used to produce all summary tables and figures and data listings.

Raw data will be presented with the same precision with which they were collected.

For summary statistics, means and medians will be displayed to one more decimal place than was determined for raw data, dispersion statistics will have two more decimal places, and the minimum and maximum will be displayed to the same number of decimal places as the raw data.

Quantitative data will be tabulated with descriptive summary statistics: arithmetic mean, standard deviation, median, minimum and maximum values, and number of observations. For categorical data, frequency tables will be provided.

For variables expressed as percent, the denominators for the calculation of percentage will be the number of subjects who had that variable assessed.

A detailed SAP describing the methodology to be used in the final analysis will be prepared before data unblinding. A change in the planned statistical analysis will require a protocol amendment only if it substantively alters the principal features of the protocol. Any deviations from the planned statistical analyses in the protocol will be fully described in the SAP.

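### Peripheral edema is an anticipated risk and a dosing criterion, but no procedure at Visits 5 to 20 requires a systematic check for it

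*Combined protocol and SAP*

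**What the plan says.** Section 1.3 gives the anticipated adverse reactions as central nervous system effects "such as dizziness and somnolence, as well as peripheral edema".

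Section 5.1.1 uses edema twice. Footnote b of Table 5.1 defines the clinically relevant TEAE that blocks escalation to include "any episode of edema or clinically significant weight gain". Once a subject is on 15 mg BID, continuation requires adequate pain control and none of the following: "moderate or severe episode of dizziness or somnolence, edema, clinically significant weight gain", or another AE that the investigator judges clinically relevant.

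Section 9.9.2 lists the extremities only under the full physical examination. That is done at Visit 1 (de novo) or Visit 4 (rollover), and at Visit 21 for everyone. For the abbreviated version, "The abbreviated physical examination should minimally include clinical evaluations of the heart and lungs", and then: "Additional systems may be examined based on any symptoms exhibited by the subject". Footnote e of the Schedule of Events (Table 17.1) assigns the abbreviated examination to Visits 5 to 20. Section 6.2.2 assigns it to Visit 4 as well for de novo subjects.

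On eliciting adverse events, Section 9.1 says: "Subjects should be questioned in a general way, without asking about the occurrence of any specific symptoms".

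**The concern.** The plan needs an edema determination but does not say how it is to be made. The paired criterion in the same footnote, weight gain, has a measurement behind it at every on-treatment visit (Sections 6.3 and 9.9.1). Edema has none.

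Two things are at stake. First, TEAEs and physical examinations are both components of the primary endpoint (Section 3.1.3), and there is no control group (Section 3.2.2). The absolute incidence is what the study delivers, so no comparison within the study can offset under-recording. Edema first noticed late also has an uncertain onset date, which matters when a subject may move from QD to BID and back. Second, sites that routinely look at the ankles and sites that do not could apply the same row of Table 5.1 differently.

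**Working it through.** The plan states no figure on this point. The check sets the sections side by side, with one visit count.

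**1. Visits without a required extremity examination.** Visits 5 to 20 number 20 − 5 + 1 = 16. The weeks in Table 17.1 agree: Week 1 (1 visit), Weeks 3 to 13 (6), Week 16 (1) and Weeks 20 to 48 (8), and 1 + 6 + 1 + 8 = 16. The Week 3 escalation visit, Visit 6, is one of them. De novo subjects also have an abbreviated examination at Visit 4, so 16 + 1 = 17.

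**2. Interval between required extremity examinations, for a subject who completes treatment.**
- Rollover: Visit 4 (Week 0) to Visit 21 (Week 52), 52 − 0 = 52 weeks.
- De novo: Visit 1 (nominally Week −3) to Visit 21, 52 − (−3) = 55 weeks. Section 6.1.1 allows screening up to 35 days before the start of treatment, so the last required look before dosing may be 5 weeks old.

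**3. Threshold of the criterion.** Footnote b counts dizziness or somnolence only if moderate or severe, but counts edema at any grade. Mild edema is therefore enough to meet the criterion, and it is the grade that a subject is least likely to volunteer.

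**4. Routes by which edema could come to light at Visit 6.**
- *Questions put to the subject.* The only one named is on pain: "After 3 weeks on the 15 mg QD dose (at Visit 6, Week 3), subjects will be asked about the adequacy of their pain control". AE questioning is general (Section 9.1).
- *Examination.* Heart and lungs are required. Other systems are optional and prompted by symptoms (Section 9.9.2).
- *Direct observation.* Section 9.1 accepts directly observed AEs, but does not say what to inspect.
- *Weight.* Taken at the visit, but an indirect and non-specific sign of edema.
- *Table 5.1 itself.* It obliges the investigator to decide whether edema occurred since the previous visit, but names no method.

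No route both is required and looks directly for edema.

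**5. Size.** The documents give no edema incidence for either dose and no proportion of edema that subjects volunteer. Any numerical estimate would be a product of assumptions, so none is given.

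**The case against.** The strongest reply is that edema is not ignored. At each visit the investigator must evaluate the subject for AEs and may observe them directly (Section 9.1). Heart and lungs is a floor, not a ceiling. Weight is taken at every on-treatment visit. Table 5.1 forces a judgment at Week 3. Subjects who withdraw are due the full examination at early termination (Sections 4.2.2, 6.4 and 9.9.2). The restriction in Section 9.1 concerns questions, not inspection, and open questioning is a legitimate way to avoid prompted reports. Dizziness and somnolence in the same footnote also rest on AE reporting.

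All of that stands, and it rules out some stronger readings. A reader might infer that edema is not looked for at all, that nobody is responsible for checking it, or that it would go unfound until Week 52. The documents do not support this: the routes above exist, and 52 or 55 weeks is only the interval between required extremity examinations in a subject who completes.

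A reader might also infer from Section 11.2, where "the denominators for the calculation of percentage will be the number of subjects who had that variable assessed", that on-treatment extremity percentages would be calculated among symptomatic subjects only. Section 11.6.5 promises a listing and a by-visit summary, without describing a table by body system. It also sends clinically significant findings to AE reporting, which is tabulated by subject in the safety set. That denominator problem is not shown.

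The reply does not supply a requirement. Permission to examine further differs from an instruction to do so. Dizziness and somnolence are symptoms that only the subject can report, whereas edema is a sign that an examiner can see.

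**Conclusion.** The point holds as a gap in ascertainment. A named risk that is also a dosing criterion has no required systematic check at 16 consecutive clinic visits, or at 17 examinations for de novo subjects. Mild edema is likely to be under-recorded, and application of the Week 3 criterion may vary between sites. The gap itself is certain from the text. Its effect on the reported incidence is unknown, and rests on the assumption that some mild edema is neither volunteered nor noticed in passing. The analysis is descriptive, so no formal test is affected. No two sections contradict each other, and nothing here questions the dosing rule. This is a cheap improvement rather than the correction of an error.

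**What to change.** In Section 9.9.2, extend the minimum content of the abbreviated examination to heart, lungs and extremities, with peripheral edema recorded as present or absent on the eCRF. Apply this at Visits 5 to 20, and at Visit 4 for de novo subjects so that their status at the start of treatment is known. Sections 6.2.2 and 6.3 already refer to Section 9.9.2 for content. State that the Visit 6 finding should be available when the existing Table 5.1 criterion is applied, and leave that criterion unchanged. Looking for a sign does not conflict with the questioning rule in Section 9.1.

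In Section 11.6.5 or the SAP, summarise examination-detected edema by visit and per subject at any time, among all subjects examined, and separately from volunteered AEs. Because clinically significant findings become AEs, edema AEs first found on examination need to be identifiable.

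The cost is one line in Section 9.9.2, an eCRF field with a marker for how the event was found, and a brief look during an examination already scheduled. No visit is added. There are three limits:
- More mild edema will be recorded, which may bring the existing dosing criterion into play more often.
- Ascertainment may differ from the preceding studies. This matters because Section 9.1 evaluates rollover AEs in the light of those studies and Section 11.6 allows the data to be combined. Separate reporting limits the problem.
- An examination sees edema present that day, not every episode since the last visit. It narrows the gap without closing it.
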